9.2.1 Modalities of Recruitment

The cohort study will be conducted by investigators at the University of California Research Center for the MotherToBaby/Organization of Teratology Information Specialists (OTIS). The OTIS Research Center conducts the cohort arm of the Vaccines and Medications in Pregnancy Surveillance System (VAMPSS) in collaboration with the American Academy of Allergy, Asthma and Immunology (AAAAI). The OTIS organization is a network of university and health department based telephone information centers serving pregnant women and health care providers throughout the U.S. and Canada ([Leen-Mitchell, 2000](#)). These services receive spontaneous telephone or other forms of electronic inquiries from women who are pregnant or considering pregnancy, as well as from health care providers, about the safety or risk associated with environmental exposures in pregnancy, including medications. Trained Teratogen Information Specialists at each site provide appropriate risk assessment and referral for all patient and health care provider callers free of charge. These services also provide a basis for collaborative research such as this study. Thus, individual Teratogen Information Services located throughout the U.S. and Canada will serve as a source of referrals not only for benralizumab-exposed pregnancies but also for similarly-ascertained pregnant women with a diagnosis of asthma but not treated with benralizumab, and similarly-ascertained pregnant women not diagnosed with asthma who have not used benralizumab nor any known human teratogen.

Other methods of raising awareness about the study include exhibiting at national, regional and local health care professional practice meetings, direct mail to health care providers, and using media, social media, and the MotherToBaby website. Because treatment with benralizumab will require expertise in treating severe asthma, these health care providers will be a particular focus of awareness activities. With the assistance of the AAAAI, providers who treat women with more severe asthma will be a priority target for awareness.

Women who are interested in learning more about the study will be referred to or will self-refer themselves to the OTIS Research Center for information. Those women who are interested and meet the study criteria as described in Section 9.2 will be invited to enroll. Women who agree to enroll will complete the oral consent process over the telephone, and will then complete the initial telephone interview. Depending on the gestational timing of enrollment, subsequent telephone interviews will be conducted according to the Schedule shown in Table 7 Section 9.6.2. Follow up interviews will be conducted by telephone, and medical records for both the women and infant will be obtained and abstracted for information to validate exposures and outcomes. The study population by definition consists of volunteers; however, they are expected to represent a wide variety of maternal age, race/ethnic background, and health status (Bakhireva, 2008; Chambers, 1996; Chambers et al., 2013; Chambers et al., 2010). The participants will reside anywhere in the U.S. or Canada. By definition, the study participants are all female, as this is a pregnancy study. Women under the age of 18 may enroll with parent/guardian consent.

Upon initiation of recruitment, the study is expected to continue recruitment for five years. Infant follow-up will continue for one year after the last live birth following recruitment of the last participant. Recruitment and enrollment for each cohort group will occur concurrently. Enrollment will be monitored monthly by the OTIS and AstraZeneca team, and adjustments made, if necessary.

Study contact information:

The toll-free phone: [REDACTED]

Website direct to the pregnancy studies is: <https://mothertobaby.org/ongoing-studies/>

Home page for the website: www.mothertobaby.org

Table 3 Recruitment Timetable

	Year 1	Year 2	Year 3	Year 4	Year 5
Cohort 1 Benralizumab- exposed group	20	40	55	55	30
Cohort 2 Asthmatic comparison group	30	60	83	83	44
Cohort 3 Non-asthmatic comparison group	30	60	83	83	44

9.3 Variables

9.3.1 Exposure definitions

Benralizumab-exposed cohort: Exposure is defined as any dose of benralizumab for any length of time from 8 weeks prior to LMP through the end of pregnancy, as reported by the mother and validated through medical record review. The 8-week cut-off prior to LMP is based upon the terminal half-life of benralizumab of approximately 15 days (clearance of benralizumab is based on five half-lives).

Exposure is defined as yes/no in the first trimester of pregnancy for major structural birth defects as the primary outcome. For this study, first trimester exposure is defined as any dose between 8 weeks prior to LMP and 13 weeks after LMP. However, exposure to benralizumab in the second (>13 weeks through 26 weeks after LMP) and third trimester (>26 weeks after LMP) will be considered for those selected major birth defects that are potentially biologically plausibly related to later pregnancy exposures, e.g., craniosynostosis. For spontaneous abortion, exposure is defined as yes/no in the first 20 weeks of gestation, and for the other secondary outcomes, exposure is defined as yes/no anytime in pregnancy.

Gestational age is determined by an algorithm using best available information. If LMP and cycle length is known, and ultrasound measures of dating are not discrepant according to standard conventions depending on the timing of the ultrasound, the menstrual period dating will be used to calculate gestational age. If the menstrual period dating is uncertain or unknown, and an ultrasound is available, the earliest (and therefore more precise) available dating ultrasound will be used. In the event of absence of any information on dating, the delivery record best estimate of gestational age will be used.

In exploratory analyses, duration of benralizumab use in pregnancy, specific gestational timing, and dose of benralizumab will be explored. In the asthmatic comparison group, duration of other asthma medications use in pregnancy, specific gestational timing, and doses will be explored.

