9.2 Setting

The study population consists of three cohorts of pregnant women (See Section 9.5 for sample size).

Participants will be recruited into the three cohorts concurrently, on the basis of the following inclusion/exclusion criteria:

Cohort 1: Benralizumab-Exposed

Inclusion Criteria:

- Currently pregnant women diagnosed with asthma who contact the OTIS Research Center and who have been exposed to benralizumab for any number of days, at any dose, and at

any time from 8 weeks before the first day of LMP up to and including the end of pregnancy.

- Eligible participants will be currently pregnant women who agree to the conditions and requirements of the study including the interview schedule and release of medical records.

Exclusion Criteria:

- Women who have had exposure to another biologic, used for any indication, anytime during pregnancy or within 8 weeks of LMP.
- Women will not be eligible for Cohort 1 if they first contact the OTIS Research Center after prenatal diagnosis of a major structural birth defect.
- Retrospective cases (outcome of pregnancy known prior to enrollment).
- Women who have enrolled in the current study with a previous pregnancy.

Cohort 2: Treated Diseased Comparison

Inclusion Criteria:

- Currently pregnant women diagnosed with asthma and exposed to asthma medications for any number of days, at any dose, and at any time from LMP up to the date of enrollment, who contact the OTIS Research Center but who were not exposed to benralizumab during pregnancy or within 8 weeks prior to LMP.
- Eligible participants will be currently pregnant women who agree to the conditions and requirements of the study including the interview schedule and release of medical records.

Exclusion Criteria:

- Women with exposure to benralizumab any time during pregnancy or within 8 weeks prior to LMP.
- Women will not be eligible for Cohort 2 if they first come in contact with the OTIS Research Center after prenatal diagnosis of a major structural birth defect.
- Retrospective cases (outcome of pregnancy known prior to enrollment).
- Women who have enrolled in the current study with a previous pregnancy.

Cohort 3: Non-Asthmatic Comparison

Inclusion Criteria:

- Currently pregnant women who contact the OTIS Research Center.
- Eligible women may potentially have been exposed to non-teratogenic agents during this pregnancy.

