- Women who agree to the conditions and requirements of the study including the interview schedule and release of medical records.

Exclusion Criteria:

- Women who have been exposed to any known teratogenic agents as determined by the OTIS Research Center (list in Annex 1) for any number of days, at any dose, from the first day of the last menstrual period up to and including the end of pregnancy.
- Women with a self-reported diagnosis of asthma, current or previous.
- Women will not be eligible for Cohort 3 if they come in contact with the OTIS Research Center after prenatal diagnosis of a major structural birth defect.
- Retrospective cases (outcome of pregnancy known prior to enrollment).
- Women who have enrolled in the current study with a previous pregnancy.

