9.7 Statistical analysis

9.7.1 Main analysis

A detailed Statistical Analysis Plan (SAP) will be prepared and finalized prior to the submission of the first interim report.

Primary Endpoint:

The primary endpoint will be major structural defects among live born infants.

The primary comparison will be between the first-trimester benralizumab-exposed group and the disease cohort receiving asthma treatment anytime in pregnancy.

Secondary comparisons for major structural birth defects will be conducted within the subgroup of pregnancies ending in live birth, spontaneous abortion, stillbirth or elective termination, excluding lost-to-follow-up, comparing first-trimester benralizumab-exposed to the treated disease cohort.

Additional secondary comparisons will be made between the first-trimester benralizumab-exposed group and the treated asthma and non-asthmatic cohort, and between the treated asthma and non-asthmatic cohorts. Further details will be specified in the SAP.

Secondary Endpoints:

Preterm Delivery: After exclusion of twins or higher order multiples, the proportion of pregnancies ending in live birth <37 weeks' gestation will be compared between the benralizumab group enrolled and exposed anytime in pregnancy prior to 37.0 weeks' gestation and the treated diseased and non-diseased cohorts enrolled prior to 37.0 weeks' gestation.

Small for Gestational Age Infants: After exclusion of twins or higher order multiples, the proportion of pregnancies ending in a live born infant \leq 10th centile of birth weight, length and/or head circumference will be compared between the benralizumab group exposed anytime in pregnancy and the treated diseased and non-diseased cohorts.

Spontaneous Abortion: For those women in all three cohorts who enrolled in the study prior to 20.0 weeks' gestation, the proportion of pregnancies ending in spontaneous abortion accounting for left truncation will be compared between those in the benralizumab group enrolled and exposed any time in pregnancy prior to 20.0 weeks' gestation and those in the treated diseased and non-diseased cohorts.

Stillbirth: The proportion of pregnancies ending in stillbirth will be compared between those in the benralizumab-exposed group and those in the treated diseased and non-diseased cohorts.

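### The 8-week pre-LMP window does not follow from its stated basis: five half-lives of about 15 days are 75 days (10.7 weeks), so some women not cleared by the protocol's own rule can enter the primary comparator as unexposed

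*Protocol*

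**What the plan says.** Section 9.3.1 defines exposure as "any dose of benralizumab for any length of time from 8 weeks prior to LMP through the end of pregnancy" and gives one reason for the length of the pre-LMP part: it is "based upon the terminal half-life of benralizumab of approximately 15 days (clearance of benralizumab is based on five half-lives". No other reason is offered, such as counting to conception or using a different half-life.

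The window is a working rule in three places that bear on the primary analysis:

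- **Cohort 1 entry and exposure (Sections 9.2 and 9.3.1).** A dose must fall no earlier than 8 weeks before LMP.
- **Primary outcome (Section 9.3.1).** For major structural birth defects, "first trimester exposure is defined as any dose between 8 weeks prior to LMP and 13 weeks after LMP".
- **Cohort 2 exclusion (Section 9.2).** The benralizumab criterion is "Women with exposure to benralizumab any time during pregnancy or within 8 weeks prior to LMP". Earlier doses do not exclude.

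Section 9.7.1 then states: "The primary comparison will be between the first-trimester benralizumab-exposed group and the disease cohort receiving asthma treatment anytime in pregnancy". That disease cohort is Cohort 2.

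**The concern.** The protocol states a half-life, a number of half-lives and a window, and the first two do not give the third. The mismatch is not confined to a background sentence, because the window decides who counts as exposed and who may serve as an unexposed comparator. A woman whose last dose falls after the 8-week limit is passed but before five half-lives have elapsed is too early for Cohort 1. She is nevertheless eligible for Cohort 2 if she used another asthma medication between LMP and enrolment. The primary comparator would then include recent users of the study drug, which in a safety study errs in the unwelcome direction, towards no difference.

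The ENCePP checklist in Annex 2 (item 5.4) also answers yes to whether exposure is classified with regard to pharmacokinetics, and it cites Section 9.3.1. The half-life sentence is the pharmacokinetic support given there.

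**Working it through.** **Inputs.** Half-life of about 15 days, five half-lives and a window of 8 weeks = 56 days (Section 9.3.1). Comparator size of 270 with outcome and 3% prevalence of major birth defects (Table 5, Section 9.5).

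**1. Try to reproduce the 8 weeks.** Washout = number of half-lives × half-life.

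- 5 × 15 = 75 days; 75 / 7 = 10.7 weeks. The stated 56 days is not reproduced.

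**2. See whether another reading gives 56 days.**

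| Reading | Result |
|---|---|
| Half-life of 14 days (assumed) | 5 × 14 = 70 days = 10.0 weeks |
| Half-life of 16 days (assumed) | 5 × 16 = 80 days = 11.4 weeks |
| Four half-lives of 15 days | 60 days = 8.6 weeks |
| Half-life needed for five to equal 56 days | 56 / 5 = 11.2 days |
| Count to conception, assumed 14 days after LMP | 56 + 14 = 70 days; 70 / 15 = 4.67 half-lives |

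None gives 8 weeks from the stated inputs, and 11.2 days is too far from 15 to be rounding.

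**3. Drug remaining at LMP.** Fraction = 0.5^(days / half-life).

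- Last dose 56 days before LMP: 56 / 15 = 3.73 half-lives; 0.5^3.73 = 7.5%.
- Last dose 75 days before LMP: 0.5^5 = 3.1%.
- Ratio: 7.52 / 3.125 = 2.4.

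**4. The gap.** Days 57 to 75 before LMP: 75 − 56 = 19 days. A woman last dosed in that span, with no dose in pregnancy, cannot enter Cohort 1 and is not barred from Cohort 2. Cohort 3 is not at issue, since its exclusions include "Women with a self-reported diagnosis of asthma, current or previous".

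**5. Possible effect on the primary comparison.** Assume a true relative risk of 2, so an exposed risk of 6%. As a worst case, assume that each gap woman carries the full exposed risk.

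- 3 of 270: comparator risk = (267 × 0.03 + 3 × 0.06) / 270 = 8.19 / 270 = 3.03%; relative risk = 6 / 3.03 = 1.98.
- 27 of 270 (an assumed extreme): (243 × 0.03 + 27 × 0.06) / 270 = 8.91 / 270 = 3.30%; relative risk = 6 / 3.30 = 1.82.

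The protocol gives no count of such women; 3 and 27 are illustrations.

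**The case against.** The best defence is that LMP is not the biologically relevant date. Conception comes about two weeks later, and the teratogen list in Annex 1, though written for non-diseased controls, mostly disregards exposure between LMP and conception. Counted to conception, 8 weeks before LMP becomes about 70 days, which is exactly five half-lives at 14 days, and the text says only approximately 15. On that reading the gap shrinks from 19 days to 75 − 70 = 5. This is a reasonable rationale, but Section 9.3.1 does not give it, it falls short at the stated 15 days, and every version of the window is anchored to LMP. It is a candidate for the corrected sentence and does not rescue the present one.

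Second, few women can fall in the gap. Maintenance dosing is every 8 weeks (Section 7), so a woman on schedule has a dose within the 8 weeks before LMP and belongs to Cohort 1. Only those who stopped or delayed, and then had no dose in pregnancy, are affected. This stands. They are still plausible: the study covers planned pregnancies, Cohort 2 recruitment emphasises severe asthma (Section 9.5), and Cohort 2, unlike Cohort 1, does not exclude other biologics, so a recent switcher can enter.

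Third, the effect is swamped by sampling error. Table 5 gives a 0.19 probability of an observed relative risk above 1.5 when the true value is 1. This also stands, and it limits the point to the definition.

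**Conclusion.** The rationale is wrong as written: the stated inputs give 75 days (70 to 80 for an assumed half-life of 14 to 16 days), not 56. It follows from the criteria that a woman last dosed 57 to 75 days before LMP, and using another asthma medication, can be counted as unexposed in the primary comparison while uncleared by the protocol's own rule.

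Two stronger inferences are not supported. A reader might conclude that the comparator is materially contaminated and the primary estimate biased. The direction would be towards no effect, but the number of such women is unknown, no passage supports a full effect at 3% to 7.5% of residual drug, and even 3 fully affected women in 270 move a relative risk of 2.00 only to about 1.98. A reader might also conclude that 8 weeks is the mistaken figure. The half-life, the number of half-lives, the window or the reference date could each be the error, and the protocol does not settle which.

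This is an inconsistency in the exposure definition that should be corrected because it fixes eligibility and is cheap to put right. It is not a threat to the study's conclusions.

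**What to change.** Reconcile the window with its rationale wherever it appears: the Abstract (study design and population) and Sections 9.1, 9.2, 9.3.1 and 9.5.

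- **At minimum**, correct the sentence in Section 9.3.1 to give the true basis of 8 weeks: about 3.7 half-lives at 15 days with about 7.5% remaining at LMP, or another reference point that is stated and produces the figure. This costs wording only.
- **If the five-half-life rule is kept**, leave Cohort 1 entry at 8 weeks and extend only the Cohort 2 benralizumab exclusion to 75 days before LMP. Women in the gap then enter neither cohort. State the limit in days, since rounding up to 11 weeks would make it 77. The cost is one changed cut-off at intake, the matching wording, and a few lost comparators.

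Widening Cohort 1 to 75 days as well is not advised, because it would add the least-exposed women to the exposed group and itself dilute any effect. Cohort 3 needs no change.

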9.3.2 Outcome definitions

- **Major Structural Birth Defects:** a major structural defect is defined and classified using the CDC coding manual (CDC, 2007), as reported by the mother and validated through the medical record. The CDC coding manual is utilized to classify defects reported through the ongoing population-based Metropolitan Atlanta Congenital Defects Program (MACDP) and is based on agreed-upon criteria by CDC investigators for major structural defects regardless of etiology. Infant medical records are abstracted by the data coordinator, and reviewed by the study manager. Final validation of the classification of

all major birth defects reported in the study will be conducted by the OTIS Co-Investigator with expertise in the diagnosis of birth defects.

- **Preterm Delivery:** preterm delivery is defined as a spontaneous or induced delivery at <37 gestational weeks, reported by the mother and validated through the medical record. Please refer to Section 9.3.1 for further description of the method for defining gestational age and therefore preterm birth.
- **Small for Gestational Age (SGA) Infants:** Live born infants who are \leq 10th centile on birth weight, length and/or head circumference for infant sex and gestational age will be considered small for gestational age. The U.S. Centers for Disease Control and Prevention (NCHS) growth charts will be used for full term infants, and preterm growth charts will be used for preterm infants (Lubchenco, 1966). The outcomes of birth weight, length and head circumference are reported by the mother and validated through the medical record.
- **Spontaneous Abortion:** Spontaneous abortion is defined as spontaneous pregnancy loss prior to 20.0 weeks' gestation. In this study, since women enroll after recognition of pregnancy, spontaneous abortions are only identified after enrollment in clinically recognized pregnancies. This outcome is reported by the mother and validated through the medical record.
- **Stillbirth:** Stillbirth is defined as a fetal death that occurs \geq 20 weeks' gestation. This outcome is reported by the mother and validated through the medical record.
- **Elective Termination:** Elective termination is defined as deliberate interruption of pregnancy by surgical or medical means.
- **Small for Age Postnatal Growth:** Postnatal growth is measured at approximately 1 year of age among live born infants and age and sex specific percentiles assigned using standard U.S. growth curves. Weight, length and/or head circumference \leq 10th centile will be considered small for age. The outcomes of postnatal weight, length and head circumference are collected from pediatric records.

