9.5 Study size

The proposed sample sizes in each of the three study groups are as follows:

- 200 women exposed to benralizumab at any time 8 weeks prior to LMP and throughout pregnancy
- 300 women with treated asthma, unexposed to benralizumab, aiming to represent the full spectrum of asthma severity with emphasis on severe patients
- 300 non-asthmatic comparison women

The sample size is considered plausible based on the experience of the OTIS research group with previous studies of asthma in pregnancy, but enrollment rates for the current study are unknown. Although it is unknown to what extent benralizumab will be used by pregnant women, experience with recruitment in the omalizumab (Xolair) EXPECT registry provides some support for the proposed sample size. In six years of recruitment, the EXPECT registry recruited 191 exposed pregnancies ([J. Namazy et al., 2015](#)).

No formal statistical hypothesis testing will be done. Point estimates of the rate ratios and associated CI's between the benralizumab exposed cohort and the unexposed cohorts will be used to evaluate the potential risk of benralizumab to mothers and fetuses.

Table 5 is included to contextualize the magnitude of reported relative risks. This outlines the probability of observing rate ratios in excess of different thresholds either by chance (i.e., when the true underlying risk ratio is 1) or when there is a true underlying increase in risk (RR of 1.2, 1.5 or 2), given the planned sample size.

- If the truth is that there is no increase in risk (true RR=1), the current study would have a relatively small probability (<20%) of reporting out an observed relative risk of 1.5 or greater.
- If the truth is that there is a doubling of risk, the current study would have a higher probability of reporting an observed RR greater than 1.5 ($\geq 70\%$), and a smaller probability of reporting out an observed RR < 1.2 ($\leq 13\%$).

Table 5 Probability that observed relative risk point estimates (exposed/unexposed) will exceed different thresholds

Outcome	Prevalence in unexposed cohort	Expected number of Exposed/ Unexposed Asthmatic cohorts		True RR	Probability observed RR exceeds X			
		enrolled	with complete outcome		X=1.2	X=1.5	X=2.0	X=3.0
All major birth defects in live born infants	3%	200/300	180/270	1	0.38	0.19	0.10	0.02
				1.2	0.51	0.29	0.16	0.04
				1.5	0.68	0.45	0.27	0.08
				2	0.87	0.70	0.49	0.18
Preterm birth	7%	200/300	180/270	1	0.30	0.10	0.02	0.00
				1.2	0.50	0.22	0.06	0.00

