				1.5	0.76	0.47	0.18	0.02
				2	0.96	0.83	0.49	0.08
SGA infant	10%	200/300	180/270	1	0.26	0.07	0.01	0.00
				1.2	0.49	0.19	0.03	0.00
				1.5	0.81	0.48	0.13	0.00
				2	0.99	0.88	0.50	0.05

Numbers in Table 5 are based on 90% of enrolled pregnancies ending in live birth with completed outcome. The effect size for all birth defects among live births is based on a prevalence of 3% in the asthmatic comparison group. The effect size for preterm birth is

based on a prevalence of 7% in the asthmatic comparison group (Bakhireva, 2008). The effect size for small for gestational age infants (SGA) is based on a prevalence of 10% in the asthmatic comparison group. Simulations were done using R to estimate the probabilities presented in Table 5.

It is projected, based on experience with the EXPECT registry that almost all benralizumab-exposed participants will have received at least one dose of the medication in the period of time from eight weeks prior to LMP to the end of the trimester and will be eligible for analysis of major structural birth defects. It is also expected that the majority of study participants will enroll in the study upon recognition of pregnancy in the first trimester; however, some will enroll after 20 weeks' gestation and therefore will not be included in the analysis of spontaneous abortion.

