Elective Termination: The proportion of pregnancies ending in elective termination will be compared between the benralizumab exposed group enrolled prior to 20.0 weeks' gestation, and the diseased and non-diseased cohorts enrolled prior to 20.0 weeks' gestation.

Small for Age Postnatal Growth: After exclusion of twins or higher order multiples, the proportion of pregnancies ending in a live born infant \leq 10th centile of postnatal weight, length and/or head circumference will be compared between the benralizumab group exposed anytime in pregnancy and the treated diseased and non-diseased cohorts.

Statistical methods:

Descriptive tables will be prepared for characteristics of each of the cohorts in each interim and final report displaying n, means, standard deviations, minimums and maximums or proportions and percentages.

For the primary endpoint of major structural defects, and for the secondary endpoints of small for gestational age infants, postnatal growth and elective termination, un-adjusted relative risk estimates will be presented together with exact two-sided 95% and 80% confidence intervals.

For the secondary endpoints of preterm delivery, spontaneous abortion, and stillbirth, survival methods will be used (Kaplan Meier) to estimate crude rates and confidence intervals accounting for gestational timing of enrollment in the study.

Adjusted analyses producing relative risks and 95% and 80% confidence intervals or hazard ratios and 95% and 80% confidence intervals, where numbers permit, will be conducted. A minimum of 30 events in the overall analysis sample is required for adjusted analysis for those outcomes assessed with logistic regression. A minimum of 20 events in the overall analysis sample is required for adjusted analysis for those outcomes assessed with Cox Proportional Hazards.

Confounders will be considered for each adjusted analysis separately, using the method of change in estimate of the effect of exposure to benralizumab by 10% or more. If one confounder is identified, direct adjustment will be performed. However, given the expected low frequency of events in a study of this size, if two or more confounders are identified in any given analysis, a propensity score approach for adjustment will be considered. Appropriateness of models will be assessed graphically and by standard statistical methods.

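### The protocol compares small size at birth and at one year as one any-of-three flag per time point, which dilutes an effect confined to one measure and hides which measure moved

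*Protocol*

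**What the plan says.** Section 9.3.2 defines small for gestational age as being at or below the 10th "centile on birth weight, length and/or head circumference for infant sex and gestational age will be considered small for gestational age". The one-year outcome is built the same way: "Weight, length and/or head circumference" at or below the 10th "centile will be considered small for age".

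Section 9.7.1 sets one comparison per time point. At birth it is the proportion at or below the 10th "centile of birth weight, length and/or head circumference will be compared between the benralizumab group exposed anytime in pregnancy" and the two comparison cohorts. At one year it is the proportion at or below the 10th "centile of postnatal weight, length and/or head circumference will be compared between the benralizumab group exposed anytime in pregnancy" and the same cohorts. Both are to be reported as unadjusted relative risks with exact 95% and 80% intervals. No comparison of weight, length or head circumference on its own is stated.

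On size, section 9.5 states: "The effect size for small for gestational age infants (SGA) is based on a prevalence of 10% in the asthmatic comparison group". Table 5 uses 180 exposed and 270 unexposed infants with complete outcome. The same section says that under a true doubling an observed RR above 1.5 has probability of at least 70%, and one below 1.2 at most 13%. It also says that no formal hypothesis testing will be done.

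**The concern.** Weight, length and head circumference say different things about fetal growth, and the study collects all three. Under an any-of-three rule, infants flagged on the two unaffected measures sit in both numerators and pull the RR towards 1. A real doubling on, say, head circumference alone would look like a modest excess, and the reader could not tell which measure produced it. The study judges safety from point estimates and intervals, so a diluted estimate can reassure too much.

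A smaller matter is the denominator. Table 6 does not require all three measures to be recorded. An infant with one recorded measure has one chance of being flagged, and an infant with three has three.

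**Working it through.** **Inputs from the protocol.** 180 and 270 infants (90% of 200 and 300); 10% SGA background; a true RR of 2 as the benchmark; reference points 1.5 and 1.2 (section 9.5, Table 5).

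**Assumptions, not in the protocol.** Each measure has a 10% background, the z-scores are normal, and the pairwise correlation ρ is 0.5 to 0.8 (0 to 0.9 was also tried).

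**Step 1: reproduce Table 5.** With x ~ Bin(180, p1) and y ~ Bin(270, p0), sum the joint probabilities over all pairs where (x/180)/(y/270) > c. For p0 = 0.10 and p1 = 0.20 this gives 0.88 at c = 1.5 and 0.98 at c = 1.2 (Table 5: 0.88 and 0.99). With p1 = p0 = 0.10 it gives 0.07 at c = 1.5 (Table 5: 0.07). All 16 SGA cells reproduce within 0.01.

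**Step 2: rate of the pooled flag.** With t_i the normal cut-off for measure i,

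P(any flag) = 1 − ∫ φ(u) ∏ Φ((t_i − √ρ·u)/√(1−ρ)) du.

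The case ρ = 0 can be checked by hand. Background is 1 − 0.9³ = 0.271. With one measure doubled it is 1 − 0.8 × 0.9² = 0.352. The ratio is 0.352/0.271 = 1.30.

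**Step 3: one measure doubled, seen through the pooled flag (180/270).**

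| ρ | Unexposed | Exposed | Pooled RR | P(RR>1.5) | P(RR>1.2) |
|---|---|---|---|---|---|
| 0.5 | 0.218 | 0.287 | 1.31 | 0.19 | 0.70 |
| 0.6 | 0.205 | 0.271 | 1.32 | 0.22 | 0.71 |
| 0.7 | 0.190 | 0.254 | 1.34 | 0.25 | 0.73 |
| 0.8 | 0.172 | 0.236 | 1.37 | 0.30 | 0.75 |

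Over ρ from 0 to 0.9 the pooled RR is 1.30 to 1.44 and P(RR>1.5) is 0.14 to 0.39. If the pooled flag itself is set to a 10% background (3.5% to 6.4% per measure), the pooled RR is 1.32 to 1.42 and P(RR>1.5) is 0.28 to 0.39. The measure alone would then give 0.72 to 0.81. The dilution does not depend on the base rate chosen.

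**Step 4: match the false-alarm rate.** With no effect, P(RR>1.5) is 0.07 for one measure but 0.01 to 0.02 for the pooled flag, because the higher base rate makes its RR less variable. A fixed cut of 1.5 is therefore stricter for the pooled flag.
- If the pooled cut is lowered until its false-alarm rate is 0.07, it detects the one-measure doubling with probability about 0.50 to 0.52.
- Looking at three separate measures, at least one exceeds 1.5 by chance with probability of about 0.16 to 0.18. At that rate the pooled flag detects the doubling with probability about 0.71 to 0.73.

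**Step 5: other effect patterns (ρ from 0 to 0.9).** If all three measures double, the pooled RR is 1.78 to 1.86 and P(RR>1.5) is 0.86 to 0.92. If one measure triples, the pooled RR is 1.60 to 2.03 and P(RR>1.5) is 0.67 to 0.95.

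**Step 6: recorded measures.** Background flag probability is 10% with one measure recorded, 14% to 17% with two and 17% to 22% with three (ρ from 0.8 to 0.5).

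**The case against.** The strongest reply has four parts.

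First, showing the components of a composite is ordinary SAP content. Section 4 leaves details of definitions to the SAP, and section 9.3.2 speaks of the outcomes of weight, length and head circumference in the plural. This stands in part: a reader might infer that the measures will never be analysed separately, and the protocol does not support that. It shows only that its own stated comparison is pooled.

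Second, the fall from 0.88 to 0.19–0.30 might be read as pure loss from pooling. It is not, because it holds the cut at 1.5 while the base rate roughly doubles (step 4). This stands. The loss at a matched false-alarm rate is smaller, though still real.

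Third, a reader might infer that growth effects in general are likely to be missed. That goes too far. The 1.5 mark is context and not a decision rule. A doubling on one measure still exceeds 1.2 in 70% to 75% of studies at ρ of 0.5 to 0.8, and a shared shift or a tripling usually shows. What remains is that an RR of 1.2 or less would arise in about 25% to 30% of studies (1 − 0.75 to 1 − 0.70), against the 13% bound that section 9.5 gives for a doubling.

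Fourth, unequal recording of measures biases the RR only if completeness differs between cohorts. Table 4 collects infant size alike in all three, and section 9.6.1 expects little missing data. This stands: it is a reason for clean denominators and not evidence of bias.

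**Conclusion.** The point holds within limits. The comparison written into section 9.7.1 turns a doubling confined to one measure into a pooled RR of about 1.31 to 1.37. It lowers P(observed RR>1.5) from 0.88 to 0.19–0.30, or to about 0.5 to 0.7 once false-alarm rates are matched. The direction held at every correlation tried. The sizes rest on an assumed 10% rate per measure, assumed correlations, and an effect on one measure that leaves two correlated measures unmoved; none of these is given in the protocol. If all three measures shift together little is lost (pooled RR about 1.8). Even then the pooled RR cannot say which measure moved. The number of infants with one-year records is not stated, so the one-year figures may be less precise. This is an inexpensive improvement to two secondary endpoints and does not affect the primary analysis.

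**What to change.** In section 9.7.1, present the RR with 95% and 80% intervals separately for weight, length and head circumference, at birth and at one year. Use as denominator the infants with that measure recorded, and keep the any-of-three composite as an additional row. If the SAP already does this, a sentence in the protocol pointing to it is enough.

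The data are already collected, so the cost is a few table rows and some wording. The real downside is more chance findings: with no effect, at least one of three measures exceeds RR 1.5 with probability of about 0.16 to 0.18, against 0.07 for a single measure. In a study without formal testing this is acceptable if the report says so beside the table.
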